6.1 Demography and baseline characteristics

Age, height, weight, systemic sclerosis characteristics, duration of systemic sclerosis, concomitant disease, concomitant medication

And all efficacy variables at baseline

6.2 Primary variable

Analyze if patients with SSc and borderline-PAP show an improvement by treatment with ambrisentan 10 mg/die over 6 months in mPAP

6.3 Secondary variables

6.3.1 Efficacy

- (1) Analyze if in patients with SSc and borderline-PAP an improvement by treatment with ambrisentan 10 mg/die over 6 months is show in:
- (2) 6-Minute-walking test
- (3) Echocardiography: right atrial area (RA-area), right ventricular area (RV-area), Tei, Tricuspid Annular Plane Systolic Excursion (TAPSE), systolic pulmonary arterial pressure (sPAP), right ventricular pump function, left ventricular pump function,

- (4) Lung function tests: forced expiratory flow (FEV_1), total lung capacity (TLC), diffusion-limited carbon monoxide (DLCo), DLCo/alveolar volume (VA), forced vital capacity (FVC), forced expiratory volume in one second (FEV_1), residual volume
- (5) Borg Dyspnea Index
- (6) WHO-functional class
- (7) further invasively measured hemodynamic parameters evaluated by RHC: right atrial pressure, pulmonary vascular resistance, cardiac output (CO), cardiac index (CI), PAWP, venous oxygen saturation (SvO_2) at rest and during exercise
- (8) Raynaud-syndrome and skin involvement, assessed by the modified Rodnan-Skin score and Symptoms of Scleroderma (descriptive)
- (9) WHO functional class
- (10) Laboratory parameters (NT-proBNP)

6.3.2 Safety/Tolerability

Adverse events, Laboratory: hemoglobin, hematocrit, AST, ALT, bilirubin, CRP, sodium, urea, creatinine, clearance, NT-proBNP

Vital signs, hospitalisations, time point from baseline and duration, Hemodynamics: Cardiac Output, venous oxygen saturation (during RHC)

6.3.3 Quality of life

Quality of life (QoL, SF-36); Two summation scores: Mental component score, Physical component score; 8 subscales: vitality, physical functioning, bodily pain, general health perceptions, physical role functioning, emotional role functioning, social role functioning, mental health.

7 Handling of missing values and outliers

7.1 Missing values

Variables with more than 20% missing values will be excluded. For all others, a complete case data analysis for each variable will be performed. No imputation method will be applied.

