### **Sample Size**

In this randomized, controlled, double-blind study patients with borderline PAH will be randomized into two groups: one group receiving ambrisentan and one Placebo. The main comparison will be the difference in treatment effect between ambrisentan arm and placebo. The primary endpoint will be the change of mean pulmonary arterial pressure between baseline and after 6 months compared to placebo.

Based on previous data and the inclusion criteria we expect a baseline mPAP of 20 mmHg, a mean reduction of 3 mmHg (equals 15%) with standard deviation of the difference of 2.5 mmHg. To reject the null hypothesis with 90 percent probability if the means of the mPAP differ by at least 3 mmHg (17 vs. 20 mmHg, 15%) a sample of 15 patients in each group is required, according to the two-tailed Student's t-test, with a type I error of 0.05 (two-sided) and equal standard deviations of 2.5 mmHg in both patient groups.

EudraCT: 2014-001882-28	3.1 Version 29.04.2016 final	EDITA
-------------------------	------------------------------	--------------

Due to the fact that the borderline-PAP-group is defined by an mPAP of 21-24 mmHg the sample will have a small standard-deviation. The effect of lowering the mPAP in SSc-APAH-patients by 15% has been reached in several studies as in Klinger et al. (2011). In order to cover a possible 20% drop-out rate, we will include 19 patients in each group = 38 patients in total.

The sample size was calculated by means of a two-sided two-sample t-test. Primary efficacy analysis will be performed by an analysis of covariance (ANCOVA) model including baseline scores as covariate, thereby yielding a power advantage over the standard t-test used for sample size calculation. The calculated sample size will thus provide 90% power or more.

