## 1.1 Flow Chart/ Trial Schedule

	Randomized; double-blind controlled study including 38 patients with “borderline-PAH”				
Assessment	Screening “borderline-PAH” day -28/-1 Visit 1*	Baseline o day 1* Visit 2	After 3 months/ 90 days ± 2weeks Visit 3	After 6 months/ 180 days ± 2weeks Visit 4*	30±7 days Follow-up by phone
Written Informed Consent, obtained before any study procedure	X				
Check of eligibility criteria	X	X			
Demographics (height)	X				
Medical History	X				
Randomization		X			
Physical Examination	X	X	X	X	
SSc characteristics		X		X	
Modified Rodnan Skin Score and Symptoms of Scleroderma		X		X	
Vital Signs (blood pressure, heart rate, oxygen saturation, body weight)	X	X	X	X	
WHO functional class	X	X	X	X	
Electrocardiogram		X	X	X	
Pulmonary function tests: DLCo, DLCo/VA, FVC, FEV1, TLC, residual volume; blood gas analysis		X		X	
Local lab assessment #	X	X	X	X	
Pregnancy test (serum or urine)	X	X	X	X	
Echocardiography	X	X		X	
Right heart catheterization** (RHC), at rest, during exercise	X			X	
Quality of life Questionnaire SF-36		X		X	
6MWD, Borg Dyspnea Index		X	X	X	
Adverse events (AE)		X	X	X	X
Concomitant medication	X	X	X	X	
Concomitant disease	X	X	X	X	X
Study medication and Diary hand out or check		X	X	X	

o In borderline-PH-patients the screening assessment of PH screening (screening study, accepted by the Ethics committee University of Heidelberg) may be used as baseline examination for the randomized, double-blind part of the study when the screening assessment is not older than 28 days.

\* according to hospital practice possible in-hospital stay

\*\* Baseline-RHC may be up to 6 months old at inclusion, continuous ECG, CO and SvO2 recording during haemodynamic investigations

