1.2 Trial design

This is a monocentric, randomized, controlled, double-blind study. Male or female SSc patients with borderline PAH will be randomized into two groups: Ambrisentan group and Placebo group. The primary endpoint will be the change of mean pulmonary arterial pressure between baseline and after 6 months compared to placebo.

2 Analysis of data quality

This analysis will be performed before unblinding the therapy arms.

1. For all variables at baseline, after 3-months and 6-months descriptive statistics mean standard deviation, median, IQR, min max, boxplot inspections of outliers for continuous variables and frequencies for categorical variables. Validation/correction will be performed by queries.

2. Calculation of differences for the parameters mPAP and all secondary endpoints. Descriptive statistics as in 1. for the differences to evaluate plausibility of the data.
3. Control of inclusion and exclusion criteria and withdrawal criteria, definition of patients to be excluded if applicable.
4. Control of laboratory values (and comparison to normal values)

3 Closure of the database and unblinding of treatment groups

1. After all data quality and plausibility checks have been performed and queries haven been answered
2. Database lock will be signed by data management, statisticians, principal investigator and trial coordinator
3. Data Transfer from open clinica to SPSS
4. Unique labeling of all major variables for the statistical Evaluation
5. Data dictionary
6. Merging of the data with the randomization list/group allocation

4 Analysis sets

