4.1 Definitions

All patients randomized and treated will be valid for the intention-to-treat analysis population. A randomized patient is valid for the intention-to-treat, if at least one dose of study medication was administered. A patient is valid for per-protocol analysis, if the patient has an adequate hemodynamic measurement at baseline and after 12 weeks or if withdrawn due to lack of efficacy, who has an adequate hemodynamic assessment at any time post-baseline up to 12 weeks, and shows no major protocol deviation.

Major protocol deviations are:

1. Patients who do not meet the inclusion criteria
2. Administration of study medication not according to protocol (e.g. compliance less than 80% or greater 120%)

The above specifications of the analysis populations are in accordance with the recommendations given in the ICH-E9 Guideline “Note for guidance on statistical principles for clinical trials”.

The safety set comprises all patients who have been included in the study.

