8.5 Efficacy Analysis primary parameter

The main parameter is the mPAP after 6 months compared to baseline. The differences will be compared between treatment and placebo group along with baseline mPAP as covariate using a covariance analysis, if the assumptions for a covariance analysis are fulfilled. Otherwise the individual differences of baseline mPAP and 6 months mPAP will be compared between therapy groups by robust comparisons of means as implemented in JMP14.

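### The SAP's rule excluding variables with more than 20% missing values does not exempt the primary endpoint; read literally, 8 missing 6-month mPAP values among 38 treated patients remove the primary analysis.

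*SAP*

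**What the plan says.** SAP 7.1 sets three rules for missing data. The first is "Variables with more than 20% missing values will be excluded". The other two are that all remaining variables are analysed by complete cases, and that nothing is imputed. No variable is exempted.

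The SAP introduces mPAP under the heading "6.2 Primary variable", within its section on analysis variables. SAP 8.5 then says: "The main parameter is the mPAP after 6 months compared to baseline". It prescribes analysis of covariance with baseline mPAP as covariate, or a robust comparison of means if the covariance assumptions fail. That is the only condition it sets; missingness is not mentioned.

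Efficacy is analysed in the intention-to-treat set (SAP 4.2), defined in 4.1: "A randomized patient is valid for the intention-to-treat, if at least one dose of study medication was administered".

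The protocol's Sample Size section says that "a sample of 15 patients in each group is required" and adds: "In order to cover a possible 20% drop-out rate, we will include 19 patients in each group = 38 patients in total". In the protocol's Flow Chart, the row "Right heart catheterization (RHC), at rest, during exercise" is marked only at screening and at the 6-month visit.

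**The concern.** A rule that drops sparsely recorded variables is ordinary housekeeping for a long list of secondary measures. Applied to the primary endpoint, it decides whether the trial has a primary result at all. On its wording it does apply to mPAP.

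The threshold also equals the drop-out allowance used to size the trial, so a loss the protocol planned for can cross it. A missed 6-month catheterization has no scheduled replacement.

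If the rule were triggered, the team would have to choose between following the SAP and having no primary analysis, or keeping mPAP as an unplanned departure from the SAP. Neither is acceptable when one sentence can settle the matter in advance.

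**Working it through.** **Inputs.** From the protocol's Sample Size section: difference 3 mmHg, SD 2.5 mmHg in each arm, two-sided alpha 0.05, power 90%, drop-out allowance 20%. From SAP 7.1: exclusion above 20% missing.

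**The protocol's sample size, reproduced.** By the normal approximation, n per arm = 2 × (1.960 + 1.282)² × 2.5² / 3² = 14.6, rounded up to 15. Allowing for drop-out, 15 / 0.8 = 18.75, rounded up to 19 per arm, or 38 in total. The exact t-test gives 88.7% power at 15 per arm and needs 16 for 90%. This small difference is not at issue here.

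**Trigger.** 20% of 38 is 7.6.
- 7/38 = 18.4%: mPAP is kept.
- 8/38 = 21.05%: mPAP is excluded.

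**Link to the planned loss.** Going from 19 + 19 to 15 + 15 means 8 missing, which triggers the rule if all 38 are dosed. If fewer are dosed, 30 evaluable patients do not trigger it: 7/37 = 18.9% and 6/36 = 16.7%. The overlap comes from rounding 18.75 up to 19, which turns a 20% loss per arm into 4/19 = 21.05%.

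**How likely.** Let p be the probability that a patient has no 6-month mPAP, independent between patients. The number missing is then binomial with n = 38. The documents give only the 20% allowance; the other rates are assumptions.

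| p | P(8 or more of 38 missing) |
|---|---|
| 5% | 0.05% |
| 10% | 3.2% |
| 15% | 20.1% |
| 20% | 50.0% |

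A patient who stops treatment may still attend the 6-month catheterization. At 20% drop-out, if 75% of drop-outs lack it, p = 0.20 × 0.75 = 15%; if 50% lack it, p = 10%. The third and second rows then apply.

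Exactly 15 + 15 remaining is only a small part of the 50%. The chance of exactly 4 missing in an arm of 19 at 20% is 0.218, and 0.218² = 4.8%. In the other 45 percentage points at least one arm is already below 15.

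**What would be discarded.** Exact two-sample t-test power uses noncentrality 3 / (2.5 × √(1/n₁ + 1/n₂)) on n₁ + n₂ − 2 degrees of freedom. For 15 + 15 the noncentrality is 3.29.

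| Evaluable | Missing of 38 | Power |
|---|---|---|
| 15 + 15 | 8 | 88.7% |
| 11 + 19 (most uneven split) | 8 | 86.4% |
| 12 + 12 | 14 | 80.2% |

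At 20% drop-out, the probability that the rule is triggered and power is still at least 80% is 0.489. As a share of triggering cases that is 0.489 / 0.500 = 98%.

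**Denominator.** SAP 7.1 does not say whether the 20% is a share of randomised or dosed patients, whether it is counted overall or per arm, or whether it refers to the 6-month value or the change. Counted per arm, 4 of 19 in one arm (21.05%) would suffice.

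**The case against.** The best counter-argument is that 8.5 is a specific instruction for the main parameter and so prevails over a general rule in 7.1. The next subsection, 7.2, names the primary and the secondary efficacy parameters expressly, whereas 7.1 does not, which could suggest that 7.1 was not aimed at the primary. This reading is reasonable and may be what the authors meant, but the SAP does not state it. Section 7.2 also shows that section 7 does reach the primary endpoint. And if 7.1 does not cover mPAP, the complete-case and no-imputation rules do not cover it either, leaving the primary endpoint without any missing-data rule.

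Second, the 20% is a recruitment allowance, not a forecast. That stands: the 50% is the top of the range shown, and at 10% missing the chance is about 3%.

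Third, missing values would be seen at the data-quality review in SAP section 2, of which the SAP says: "This analysis will be performed before unblinding the therapy arms". A decision to keep mPAP could therefore be taken blind to treatment. That limits the harm, but the decision would still be ad hoc.

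Finally, SAP 4.1 mentions hemodynamic assessments up to 12 weeks in patients withdrawn for lack of efficacy. That clause concerns the per-protocol set and does not supply a 6-month value.

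**Conclusion.** The point holds and should be fixed. As written, the 20% rule covers the primary endpoint, and followed literally it would remove the mPAP analysis at 8 or more missing of 38 treated patients. What is established is that no exemption is written; whether the team would actually drop the analysis depends on which reading it adopts.

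The 3% to 50% range for reaching the trigger, at 10% to 20% missing, rests on independent losses and all 38 being dosed. The power figures rest on the protocol's 3 mmHg and SD of 2.5 mmHg. They show that the discarded analysis would usually still be informative, but they say nothing about bias from missing data.

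**What to change.** In SAP 7.1:

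1. State that the 20% exclusion rule does not apply to the primary endpoint (mPAP at 6 months and its change from baseline). It is analysed on available data by the method in SAP 8.5, with the number of missing 6-month catheterizations and the reasons reported per arm.
2. Name the denominator of the rule for the variables it still governs, for example the treated intention-to-treat set.

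The cost is two sentences and one small table, with no new patients, visits, procedures or models. The downside is that with much missing data a complete-case result may be biased, so it must be interpreted together with the reported missingness. Whether to add a missing-data sensitivity analysis for mPAP, and whether to keep the rule for secondary variables, is for the sponsor's statistician to decide.

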7.2 Outliers

Definition: outliers and extreme values (according to boxplots)

The primary and all secondary efficacy parameters and their difference between baseline and 6 month visit will be analysed whether there are outliers or extreme values in the respective medication group. Outliers are defined as values that are larger than $Q75+1.5*IQR$ or lower than $Q25-1.5*IQR$; extreme Values are defined as values that are larger than $Q75+3*IQR$ or lower than $Q25-3*IQR$.

8 Statistical analyses / methods

8.1 Subject disposition

Systemic sclerosis severity (modified Rodnan Skin score; disease duration; type of systemic sclerosis; systemic sclerosis characteristics including presence of digital ulcers, calcinosis, dysphagia, teleangiectasia, Raynaud phenomenon, joint pain), hemodynamics at baseline (mPAP at rest and during exercise, achieved workload, cardiac index and cardiac output) and WHO-FC will be analyzed descriptively within the therapy groups and compared. Changes during the study will be analysed descriptively.

8.2 Demography and baseline characteristics

All variables (demographic and other baseline characteristics, continuous data at each visit and their change to baseline) will be characterized by arithmetic mean, median, standard deviation, standard error, 95% confidence limits of mean, median, first and third quartiles, minimum, and maximum for quantitative variables. Frequency tables for qualitative data will be provided.

8.3 Prior or concomitant medication and diseases

Frequencies by organ system and duration, difference between therapy groups.

8.4 Exposition to treatment/Compliance

Frequencies and duration of intake or application, difference between treatment groups will be analysed. A compliance between 80-120% will be defined as target level.

8.5 Efficacy Analysis primary parameter

The main parameter is the mPAP after 6 months compared to baseline. The differences will be compared between treatment and placebo group along with baseline mPAP as covariate using a covariance analysis, if the assumptions for a covariance analysis are fulfilled. Otherwise the individual differences of baseline mPAP and 6 months mPAP will be compared between therapy groups by robust comparisons of means as implemented in JMP14.

8.6 Analysis secondary parameters

No subgroup analyses and interim analyses planned.

8.6.1 Efficacy

Secondary efficacy analysis comprises hemodynamics, vital signs, electrocardiogram, echocardiography, systemic sclerosis characteristics, laboratory parameters, pulmonary function, 6-minute walking distance, quality of life scales. For continuous variables the therapy groups will be compared with the same methods as for the primary parameter.

WHO functional class is supposed to either remain the same, improve by one or two categories, or deteriorate by one category in most cases. A change score (baseline minus end of study) will be calculated, which could go from -3 (class 4 at baseline and class 1 at end of study) to +1 (class 3 at baseline and class 4 at end of study). This will be analyzed using the Wilcoxon test.

For categorical variables Mc Nemar Tests will be applied.

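### WHO functional class is tested on raw change without regard to baseline class; a rank-sum test stratified by baseline class needs no new data and usually gains power, and the test and the sign of the score should be clarified in the same edit

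*SAP*

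**What the plan says.** SAP 8.6.1 handles WHO functional class separately from the other secondary variables. It describes the movement it expects: "WHO functional class is supposed to either remain the same, improve by one or two categories, or deteriorate by one category in most cases". It then defines the variable: "A change score (baseline minus end of study) will be calculated". The stated range runs from minus "3 (class 4 at baseline and class 1 at end of study) to +1 (class 3 at baseline and class 4 at end of study". The test is given in one sentence: "This will be analyzed using the Wilcoxon test". No baseline stratum or covariate is mentioned.

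The same section treats continuous secondary variables differently: "For continuous variables the therapy groups will be compared with the same methods as for the primary parameter". Under SAP 8.5 that method compares the arms "along with baseline mPAP as covariate using a covariance analysis", provided the model's assumptions are met. Otherwise the individual differences are compared by robust methods. The Protocol's Sample Size section credits baseline adjustment with a power advantage over the t-test.

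The trial schedule (Protocol 1.1) has a row for "WHO functional class" at screening, baseline, month 3 and month 6.

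**The concern.** On a four-level scale the possible change is fixed by the starting class. Taking month 6 minus baseline, so that negative is better:

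| Baseline class | Possible change |
|---|---|
| I | 0 to +3 |
| II | -1 to +2 |
| III | -2 to +1 |
| IV | -3 to 0 |

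A patient who stays in class I has the best result open to them and scores 0. A patient who stays in class III also scores 0, although improvement was possible. An unstratified test puts all these scores on one common ranking, so differences in starting class enter the treatment comparison as noise. At stake is efficiency on a named secondary endpoint in a trial of 38 patients.

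The wording has two further problems.

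- **Which Wilcoxon test.** Rank-sum compares the arms. Signed-rank tests change within an arm and does not compare them. The next sentence of the SAP assigns McNemar tests, which are also paired, to categorical variables, so context does not settle the question.
- **The sign.** The definition of the score and its worked examples point in opposite directions.

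**Working it through.** **1. Sample size available.** The documents give no power statement for WHO class, so the only figure to reproduce is the primary one. Inputs from the Protocol's Sample Size section: difference 3 mmHg, 90% power, and the test set up "with a type I error of 0.05 (two-sided) and equal standard deviations of 2.5 mmHg in both patient groups".

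n per arm = 2(1.960 + 1.282)² × 2.5² / 3² = 14.6, so 15. With 20% drop-out, 15 / 0.8 = 18.75, so 19. Both stated figures reproduce. (The exact noncentral t gives 88.7% power at 15 and 90.7% at 16, an immaterial difference here.) SAP 7.1 uses complete cases, so WHO class will have about 15 to 19 patients per arm.

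**2. Sign of the score.** By the definition, class 4 to class 1 is 4 - 1 = +3, and class 3 to class 4 is 3 - 4 = -1. The SAP prints -3 and +1, which are 1 - 4 and 4 - 3, that is, end minus baseline. A two-sided rank-sum p-value is unaffected, but the reported direction of change would flip.

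**3. The two tests.** For baseline stratum h with N_h patients, n_1h on ambrisentan and n_0h on placebo, let W_h be the rank sum of the changes on ambrisentan.

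- E_h = n_1h(N_h + 1)/2
- V_h = (n_1h n_0h / 12) × [(N_h + 1) - Σ(t³ - t)/(N_h(N_h - 1))], where t runs over the sizes of the tied groups
- Unstratified: one stratum holding everyone, Z = (W - E)/√V
- Van Elteren: w_h = 1/(N_h + 1), Z = Σ w_h(W_h - E_h) / √(Σ w_h² V_h)

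Within a stratum, ranking the change is the same as ranking month-6 class. If n_1h or n_0h is zero, V_h = 0 and the stratum contributes nothing.

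**4. Latent-normal simulation (all inputs assumed).** Baseline and month-6 severity are correlated normals cut into four classes, with the ambrisentan arm shifted towards better classes. The test is two-sided at 5%. Power for an assumed mix I/II/III/IV of 15/50/33/2% and a shift of 0.9 SD:

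| Correlation | 15 per arm, unstratified → stratified | 19 per arm, unstratified → stratified |
|---|---|---|
| 0.4 | 43 → 56% (+13) | 55 → 70% (+15) |
| 0.6 | 54 → 65% (+11) | 64 → 75% (+11) |
| 0.8 | 72 → 77% (+5) | 82 → 88% (+6) |

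Mixes of 30/60/9/1% and 10/75/14/1% were added. Over all 18 cells the gain was 4.7 to 16.5 points in one run and 5.3 to 18.6 in a repeat with 4,000 trials per cell. The Monte Carlo standard error of a power near 50% with 4,000 trials is √(0.25/4000) = 0.8 points. Varying the assumptions gave:

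- shift 0.5 SD, correlation 0.4 to 0.8: 0.8 to 7.6 points;
- correlation 0.95, either shift: about -3 to +5 points. The worst cell in a smaller run (mix 10/75/14/1%, 15 per arm, shift 0.5 SD) fell from 31.5% to 27.5%, a loss of 4.

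**5. Other outcome models (also assumed).** Proportional-odds and one-class-step models gave -3 to +12 points at 15 per arm and -2 to +10 at 19. Explicit transition tables, graded by how strongly change depends on baseline class, gave these powers:

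| Dependence | 19 per arm, I/II/III = 20/50/30% | 15 per arm, I/II/III = 5/80/15% |
|---|---|---|
| Mild | 38.2 → 39.5% (+1.3) | 35.6 → 33.6% (-2.0) |
| Moderate | 55.0 → 60.6% (+5.6) | 53.9 → 53.3% (about -0.5) |
| Strong | 61.1 → 78.7% (+17.6) | 63.7 → 69.4% (+5.7) |

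The small losses come from sparse strata. At 15 per arm a 5/80/15% mix means 0.75, 12 and 2.25 patients expected per class and arm.

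**6. Type I error.** Across these settings it was about 2 to 6% for both tests.

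**The case against.** The strongest reply is that nothing here is an error. Under randomisation a rank-sum test on the change is valid, and chance imbalance in baseline class is already covered by its null distribution. That stands. A reader might infer that the plan biases the comparison, and the documents do not support that reading.

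A reader might also attach one fixed figure to the gain, such as 5 to 17 points. That does not stand either. The documents state no class mix, effect or transition rates for WHO class. The largest gains in the latent-normal model come from correlation 0.4, where, with the 15/50/33/2% mix, 52% of placebo patients change class within six months. Nor is the change free of cost, since sparse strata can lose a few points.

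The contrast with the other endpoints should not be pressed too far. SAP 8.5 uses ANCOVA only if its assumptions hold and otherwise compares individual differences without a baseline term, so an unadjusted comparison of change has a precedent in the plan.

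Finally, this is one of many secondary variables in a phase IIA proof-of-concept trial, and SAP section 10 only screens such variables for whether they support the primary result. That limits the severity. It does not remove the reason to make a one-sentence change that uses data in hand.

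**Conclusion.** The point holds as an efficiency improvement with a clarification attached. The plan ignores baseline class where baseline class limits the outcome, and a stratified test usually does better at the same type I error. The size depends on assumptions that the documents cannot settle:

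- about +5 to +18 points for a large effect (0.9 SD, correlation 0.4 to 0.8);
- about +1 to +8 for a moderate effect (0.5 SD);
- from a loss of about 3 to 4 to a gain of about 5 when few patients change class for reasons other than treatment. Results also stay near zero when most patients share one class and change depends only weakly or moderately on it.

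Very strong dependence on baseline class would give more than 18 points in some mixes.

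A reader might infer from the bare word Wilcoxon that a within-arm signed-rank test is planned. The SAP does not say so; it leaves the choice open. The sign contradiction is certain and rests on no assumption. Severity is minor.

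**What to change.** In SAP 8.6.1, replace the test sentence with:

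> The arms will be compared by a Wilcoxon rank-sum test of the change in WHO class, stratified by baseline WHO class (van Elteren).

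In the same edit, make the definition and the examples of the change score agree. Month 6 minus baseline would match the values already printed. State that the stratum is the class at the baseline visit, because class is also recorded at screening. Ordinal logistic regression of month-6 class on arm and baseline class is an acceptable alternative.

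The cost is one or two sentences and a few lines of code, with no extra patients, visits or data. Confirm that the software in SAP section 11 runs the stratified test, or name the code that will. The statistical downside is that small strata, or a baseline class present in only one arm, contribute little or nothing and can cost a few points of power. If sparse classes are to be pooled, decide that before unblinding.

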8.6.3 Quality of life

Quality of life scales (QoL, SF-36) are secondary efficacy parameters. Their change from baseline to 6 months will be compared with the same methods as for the primary parameter.

9 Deviations from the protocol

Description and explanation of deviations regarding withdrawal criteria, in- and exclusion criteria, adherence to time window and treatment compliance will be provided.

Major protocol deviations are:

1. Patients who do not meet the inclusion criteria

2. Administration of study medication not according to protocol (e.g. compliance less than 80% or greater 120%); Discrepancies of study medication intake are noted as comments in the CRF.

10 Interpretation of results

Effect size estimation and description

Clinical worsening on the individual level is defined as 15% higher mPAP values at 6 months compared to baseline. Clinically significant improvement is defined as 15% lower mPAP values at 6 months compared to baseline.

Scatterplots of baseline versus 6-month measurements will be plotted with a linear fit for therapy. In case of outliers or extreme values robust fits will be used. Frequency tables with patients who have a clinically relevant worsening/improvement after 6 months of therapy will be displayed.

Descriptive analysis of differences of secondary parameters.

Secondary efficacy parameters will be screened whether they support the results of the primary endpoint or not.

11 Software

SPSS V24, SAS JMP 14

12 References

https://www.jmp.com/en_us/support/online-help.html

(last queried 17.7.2018)

<https://www-01.ibm.com/support/docview.wss?uid=swg27047033>

(last queried 17.7.2018)

13 Appendices

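### Categorical secondary efficacy variables get only McNemar, a before-after test that does not compare the arms, and the WHO-class change formula contradicts its own two examples

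*SAP*

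**What the plan says.** SAP 1.2 describes the trial thus: "This is a monocentric, randomized, controlled, double-blind study". It has two groups, ambrisentan and placebo. SAP 8.6.1 sets the secondary efficacy methods by type of variable:

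- **Continuous:** "For continuous variables the therapy groups will be compared with the same methods as for the primary parameter".
- **WHO functional class:** "A change score (baseline minus end of study) will be calculated, which could go from -3 (class 4 at baseline and class 1". Here class 1 is the final status. The upper limit is given as +1, illustrated by a move from class 3 to class 4. The test follows: "This will be analyzed using the Wilcoxon test".
- **Categorical:** "For categorical variables Mc Nemar Tests will be applied".

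The list of secondary efficacy domains in 8.6.1 includes the electrocardiogram, echocardiography and systemic sclerosis characteristics. SAP 8.1 covers the same sclerosis characteristics, among them digital ulcers, calcinosis and dysphagia, and says of them: "Changes during the study will be analysed descriptively". SAP 6.3.1 and the protocol's Secondary Endpoints label Raynaud, skin score and scleroderma symptoms as descriptive. SAP section 10 (Interpretation of results) adds: "Secondary efficacy parameters will be screened whether they support the results of the primary endpoint or not".

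**The concern.** McNemar's null hypothesis is that, within one set of patients, as many change in one direction as in the other. Treatment arm does not enter it. Pooled over arms, the test ignores randomisation. Run in each arm, it yields two change-from-baseline tests, and finding one significant and the other not is no test of the difference between them. The SAP does not say which use is meant. It promises a comparison of therapy groups only for continuous variables.

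The WHO-class rule has a separate fault: the formula and its examples have opposite signs. Someone who codes the formula but reads the output by the examples would report improvement as worsening. In addition, the named test could be the rank-sum test, which compares arms, or the signed-rank test, which repeats the McNemar problem.

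At stake is the use of secondary results as support for the primary finding. A before-after p-value for a categorical variable cannot provide that support.

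**Working it through.** **1. Is there a between-arm test elsewhere?** SAP 8.1 speaks of description within groups and of comparison, but names no test. SAP 8.3 and 8.4 concern concomitant medication and diseases, and compliance. SAP 8.6.2 is descriptive safety tabulation. SAP section 10 gives frequency tables of 15% worsening or improvement in mPAP without a test. The protocol's Statistical Analysis section names no method for categorical efficacy variables. So there is none.

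**2. Which variables are exposed?** WHO class has its own test, most variables in SAP 6.3.1 are numeric, and Raynaud, skin score and scleroderma symptoms are descriptive. That leaves mainly the systemic sclerosis characteristics (efficacy in 8.6.1, descriptive in 8.1) and any ECG or echocardiography finding recorded as a category.

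**3. WHO-class arithmetic.**

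| Example | SAP prints | Baseline minus end | End minus baseline |
|---|---|---|---|
| Class 4 to class 1 | -3 | 4 - 1 = +3 | 1 - 4 = -3 |
| Class 3 to class 4 | +1 | 3 - 4 = -1 | 4 - 3 = +1 |

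The stated formula reproduces neither figure; the reverse subtraction reproduces both. Reversing every sign leaves a two-sided rank-sum p-value unchanged (0.738 either way when 6/19 versus 5/19 improve by one class).

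**4. Worked tables, 19 per arm** (the planned group size in the protocol's Sample Size section). With b patients improved and c worsened, the exact two-sided McNemar p-value is the two-sided binomial probability of b out of b + c at 0.5. The between-arm test is Fisher's exact test on change category.

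| Arm A (improved/worsened) | Arm B (improved/worsened) | McNemar A | McNemar B | McNemar pooled | Fisher between arms |
|---|---|---|---|---|---|
| 6/0 | 5/0 | 2 × 0.5^6 = 0.031 | 2 × 0.5^5 = 0.063 | 2 × 0.5^11 = 0.001 | 1.0 |
| 5/0 | 0/5 | 0.063 | 0.063 | 1.0 | 0.003 |

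**5. How often this misleads when the arms do not differ.** The documents give no change rates, so the rates here are assumptions: the same in both arms, improvement 10, 15, 20, 30, 40 or 50%, worsening 2 or 5%. The calculation is exact enumeration of the exact McNemar test at two-sided 0.05. If P is the chance of significance in one arm, the chance that only the active arm is significant is P × (1 - P). The sample sizes are 15 per arm (the protocol's requirement before drop-out) and 19.

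| Improve / worsen | n per arm | Active arm only significant | Pooled significant |
|---|---|---|---|
| 10% / 5% | 15 | 0.1% | 2.2% |
| 10% / 2% | 15 | 0.2% | 4.6% |
| 20% / 5% | 15 | 3.5% | 24% |
| 30% / 2% | 15 | 18% | 78% |
| 40% / 2% | 15 | 25% | 95% |
| 50% / 5% | 15 | 24% | 95% |
| 50% / 2% | 15 | 19% | 99% |
| Whole grid | 15 | 0.1% to 25% | 2% to 99% |
| Whole grid | 19 | 0.4% to 25% | 4% to 99.9% |

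The between-arm Fisher test on improved/unchanged/worsened, at 15 per arm with 10, 30 or 50% improving, rejects in 1.0% to 2.8% of such trials. It stays below the nominal 5%.

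**The case against.** The strongest reply is that little depends on the McNemar sentence. If SAP 8.1 governs the sclerosis characteristics, only categorical ECG or echocardiography findings remain, and no section defines one. SAP section 10 also announces a descriptive analysis of differences in secondary parameters and does not say that the screening rests on p-values. The protocol calls the trial a phase IIA proof of concept. This stands as a limit on weight, but it does not make the sentence right: 8.6.1 still lists the characteristics under efficacy, and the two sections disagree.

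A second reply is that the percentages depend on one-sided change. With symmetric change of 5, 10 or 20% each way, pooled McNemar rejects in only 0.2, 1.3 and 2.4% of trials (n = 30), and the within-arm test in 0.007% to 1.3% (n = 15). That is correct, and the high pooled figures need a pooled reading that the SAP does not state. The rates illustrate and do not forecast. Symmetric change is McNemar's own null hypothesis, so low rejection there does not make it a comparison of arms.

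The worked tables also sit near the threshold. With 6 improving against 6 worsening, the within-arm tests each give 0.031, in opposite directions, and only the pooled test misses the contrast (p = 1.0). That is fair, but a reader would still be contrasting two separate p-values without a test of the difference.

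Lastly, Fisher on change categories ignores baseline status, and a patient without a finding cannot improve. Randomisation keeps the test valid, but a baseline-adjusted method is a reasonable alternative.

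**Conclusion.** The concern holds. The McNemar rule is wrong as written for a parallel-group comparison, and reading it as within-arm description leaves categorical efficacy variables with no between-arm test. The WHO-class formula is wrong by plain arithmetic on both of its examples, and the Wilcoxon variant needs naming.

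The size is moderate. Few secondary variables are affected. The WHO sign error does not change a two-sided p-value but can reverse which direction is read as improvement. The primary analysis and sample size are untouched. The table arithmetic and the WHO contradiction need no assumption about rates; the error percentages rest entirely on the assumed change rates. The plan should be corrected, but this point does not threaten the main conclusion of the trial.

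**What to change.** In SAP 8.6.1, replace the McNemar sentence with: *Categorical variables: the change category (improved, unchanged, worsened) from baseline to 6 months will be compared between therapy groups by Fisher's exact test. McNemar tests, if shown, are within-arm description only.* Define for each variable what counts as improved. If adjustment for baseline status is wanted, exact logistic regression is an option.

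State in both 8.1 and 8.6.1 which systemic sclerosis characteristics are tested this way and which are descriptive only.

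Define the WHO-class change as end of study minus baseline, with negative values meaning improvement, so that both printed examples become correct. Name the test as the Wilcoxon rank-sum test between arms.

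The cost is a few SAP sentences, with no change to data collection or sample size. The trade-off is fewer nominally significant before-after results.
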